5.0 CLINICAL AND LABORATORY EVALUATIONS

5.1 Baseline/pretreatment Evaluations

- History and physical and evaluation of patient's ability to perform daily activities (Zubrod performance status; Karnovsky or ECOG performance status may be used to estimate Zubrod) ≤ 8 weeks prior to signing consent.
- Blood tests: 4 tubes of blood will be drawn ≤ 3 month prior to protocol entry unless otherwise indicated:
 - PSA Level
 - Testosterone level - Serum testosterone will be drawn ≤ 4 months before signing consent or after enrollment but before the first radiation treatment and is within 40% of normal assay limits using the formula $x=0.4*\text{lower assay limit}$ and $x=0.4*\text{upper assay limit} + \text{upper assay limit}$). This is only applicable to patients not started on ADT prior to signing consent. Patients who have been started on ADT prior to signing consent are not required to have a serum testosterone at this level prior to signing consent; but, a serum testosterone prior to fiducial marker placement is recommended.
 - Liver function tests are within 40% of normal assay limits, as defined by the equation for testosterone.
 - Complete blood cell counts are within 40% of normal assay limits, as defined by the equation for testosterone.
 - Lipid profile (no assay limit)
- Bone scan (depending on PSA level and Gleason score) ≤ 4 months prior to signing of consent. A questionable bone scan is acceptable if other imaging studies are negative for metastasis.
- Multiparametric MRI of prostate/pelvis at 1.5T or 3.0T MRI scan ≤ 3 months prior to protocol entry.
- Gold marker placement and prostate biopsies (if patient opts to have biopsies) within 4 weeks after enrollment.
- A pathology review at the University of Miami of prostate biopsies.
- Prior to fiducial marker placement, research fluids including plasma and serum (4 tubes), and 50 ml urine will be obtained.
- CT and MRI simulation.
- Quality of Life surveys will be administered after enrollment and prior to fiducial marker placement:
 - The Expanded Prostate Cancer Index Composite Questionnaire-SF12 (EPIC-SF12)
 - Memorial Anxiety Scale for Prostate Cancer patients (MAX-PC)

- International Prostate Symptom Score (IPSS) will be administered pre-treatment.

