radiation to normal tissues, depending on tumor location, as it is delivered via a single beam that must pass through normal tissues to reach its target. Most importantly, the highest-dose regions of the grid are superficial, and often are outside of the tumor target itself. Unnecessary high dose exposure to the surrounding normal tissue can be significantly reduced by reconfiguring the grid treatment into a 3D dose LATTICE, a new approach to spatially fractionated radiation which takes advantage of modern-era technology. This technique can be used to place high-dose islands within the tumor target only, not outside of the target. Using this technique, high doses of radiation are concentrated cylinders within the tumor volume, with drastically lower dose in-between (peak-to-valley effect) and leaving anything outside of tumor volume minimally exposed. Because more pronounced radiation dose peaks and valleys are generated using LEAD technique compared to GRID, it may be more radiobiologically effective, with significantly less radiation dose to adjacent normal tissues, and therefore should confer less additional toxicity. A conceptual comparison between the two techniques as applied to the prostate is shown in **Figure 2**.

Despite the existing data from radiobiological investigations of spatially fractionated radiotherapy, its use in the clinical setting is limited. As described above, none of the publications on this technique involve patients followed in a prospective fashion, and links between biology and clinical outcome have been inadequately studied.

Based on this background information, the central hypothesis of this proposal is that a single fraction of high-dose radiation delivered via LEAD technique will mediate induction of TNF- α , TRAIL, PAR-4, and ceramide, potentially synergizing the effect of conventional fractionated radiation, without adding toxicity above that expected with standard intensity modulated radiotherapy (IMRT). Single fraction priming high dose LEAD radiation is proposed to enhance tumor cell kill via bystander (local) and abscopal (distant) effects on non-irradiated tumor cells. We anticipate that LEAD RT in combination with a subsequent clinically standard fractionation and dose of radiation will improve control of bulky prostate cancers locally and possibly impact occult micro-metastatic disease thereby leading to gains in patient survival.

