4.12 Protein biomarkers and immune activation markers in the serum/whole blood

We will assess protein biomarkers and immune activation markers in the serum/whole blood samples of patients receiving high-dose LEAD RT. Samples taken from subjects will be analyzed for activation of peripheral immunity; we will analyze B and T cell activation-specific cell surface markers (CD19, B220, CD40, CD27, CD28, CD30, CD37, CD38, CD43, and surface IgG, IgM, and IgD; CD4, CD8, HLA-DR, CD11b, CD25, CD38, CD45RO, CD134, CD150, CRTAM, FOXP3, Ly-m22 by FACS), transcription (AID, I κ B α ; granzyme, perforin, HLA-DRA by RT-PCR) and secreted cytokines (IgG, IgM; sIL2R, neopterin, sCD4, sCD8, TNF α , IL-1b, IL-2, IL-6 by ELISA) before and after irradiation. To this end, an additional 10 cc of peripheral blood will be collected after the LEAD RT treatment at about 24 hr. (\pm 12 hr.) following the procedure. One tube of whole blood from patients will be collected into an anticoagulant tube (EDTA). Buffy coat and plasma will be isolated by centrifugation. Plasma will be frozen at -80°C until analysis. PBMCs will be isolated from buffy coat on a ficoll gradient and frozen in RPMI (+40% FBS, 10% DMSO) until analysis. The second tube will be the 7-mL Vacutainer SST Gel & Clot Activator Plus Plastic (BD). Blood collected tubes will be gently inverted to evenly mix the clot activator and will be kept at room temperature for 1 hr for serum separation and will be shipped to [name] lab for ELISA. The whole blood will be shipped to [name] laboratory. The results of the biomarker confirmation will be correlated with clinical response.

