- ^dSerum testosterone will be drawn as part of routine workup ≤ 4 months before signed consent or after enrollment but prior to the first radiation treatment and must be within 40% of normal assay limits, defined as $x=0.4$ *lower assay limit and $x=0.4$ *upper assay limit + upper assay limit. Patients who have been started on ADT prior to signing consent are not required to have a serum testosterone at this level; but, a serum testosterone prior to fiducial marker placement is recommended. Serum testosterone will be drawn at the end of RT, 6 weeks, 3 months, and 9 months after radiotherapy. If testosterone remains abnormally low, tests will continue to be done at each follow-up visit.
- ^eAfter enrollment (registration) and prior to fiducial marker placement.
- ^f International Prostate Symptom Score will be administered pretreatment, at the end of treatment and at each follow-up visit.
- ^gAndrogen deprivation therapy (ADT) for applicable patients: ADT is recommended to be initiated after fiducial marker placement. Anti-androgen treatment is recommended to begin 1-14 days before LHRH agonist start. ADT may occur up to 2 months prior the signing of consent (timing is relative to LHRH agonist injection). If not started prior to consent, ADT is recommended to start after fiducial marker placement and prior to radiotherapy start.
- ^hAfter enrollment and prior to fiducial marker placement 2-4 tubes of blood and 50 mL of urine will be collected, as described in Sections 4.11, 4.12 and 5.0 for research studies.

Note: Measurements and visits during treatment should occur \pm 3 days; measurements and visits during follow-up should occur \pm 2 weeks up to the 3 month visit and \pm 4 weeks for subsequent measurements/visits, with the exception of the post-LEAD RT lipids and blood & urine collection for research, which is 24 hr \pm 12 hr.

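### The before/after-LEAD blood marker comparison has no sample just before LEAD, so the change mixes LEAD with seed placement and, in some men, biopsy, ADT start or the first IMRT fraction

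*Combined protocol and SAP*

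**What the plan says.** Section 4.12 lists cell-surface, transcription and secreted markers to be measured on both sides of irradiation. The soluble panel ends with "neopterin, sCD4, sCD8, TNF α , IL-1b, IL-2, IL-6 by ELISA) before and after irradiation". The section fixes only the later sample: "an additional 10 cc of peripheral blood will be collected after the LEAD RT treatment at about 24 hr", with a window of 12 hours either way. It does not say when the earlier sample is drawn.

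Section 5.1 supplies that timing: "Prior to fiducial marker placement, research fluids including plasma and serum (4 tubes), and 50 ml urine will be obtained". Appendix I, footnote h, gives the same timing, points to Section 4.12, and allows 2 to 4 tubes where Section 5.1 has 4. The Appendix I calendar has one pre-RT column for research fluids and then the 24-hour post-LEAD column. It shows no draw on the day of LEAD.

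On ADT, footnote g of Appendix I says: "If not started prior to consent, ADT is recommended to start after fiducial marker placement and prior to radiotherapy start". Section 4.15 also lets the LHRH agonist begin up to two months before consent, and ADT is optional throughout.

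The rationale (Section 1.4.5) gives as its central hypothesis that one LEAD fraction "will mediate induction of TNF- α , TRAIL, PAR-4, and ceramide". This sentence is not among the two numbered hypotheses at the front of the protocol, nor in the objectives in Section 2. Section 14.2 specifies no analysis of the blood markers.

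**The concern.** The markers in Section 4.12 are inflammatory and immune (TNF-alpha, IL-1b, IL-6, sIL2R, T- and B-cell activation). They are meant to show what one LEAD fraction does. If the earlier sample is taken before a transrectal needle procedure, and in some men before hormonal treatment, the difference between samples carries those effects as well. Section 1.2 describes a single-arm trial, so no comparison group can remove them. The result could be an apparent LEAD effect that is not one, or a real effect that is hidden. Section 4.12 then plans to correlate the results with clinical response. A missing sample cannot be recovered later, whereas an assay can still be run on stored material.

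**Working it through.** The plan gives no sample size, effect size or power for this comparison, so there is no figure to reproduce. The check is a timeline.

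**What falls between the two draws**

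| Event | Who | Timing | Source |
|---|---|---|---|
| Baseline research draw | All | After enrollment, before fiducials | 5.1; Appendix I, footnote h |
| Placement of 3-4 gold seeds | All treated | Within 4 weeks of enrollment | Schema; 4.3; 4.15 |
| Biopsy, up to 14 cores | Those who accept | Same procedure | Schema; 4.3 |
| Antibiotics | At the urologist's discretion | Around the procedure | 4.3 |
| ADT start | Men who begin it in the recommended window | After fiducials, before RT | Appendix I, footnote g |
| Planning MRI, then CT and planning | All | MRI at least 1 week after fiducials | 4.6 |
| LEAD | All treated | Day 1 | 4.8 |
| First 2 Gy IMRT fraction | All treated | Within 32 hr of LEAD | Schema; 4.8; 4.15 |
| Post-LEAD draw | All treated | 24 hr, plus or minus 12 hr | 4.12; 5.3 note; Appendix I note |

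**Length of the gap.** Baseline draw to fiducials is 0 to 4 weeks. Fiducials to planning MRI is at least 1 week. MRI to LEAD is not stated. The gap from baseline to LEAD is therefore at least 1 week, with no upper limit.

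**ADT in that gap.** Section 4.15 allows the LHRH agonist to start as late as 2 weeks after fiducials. Section 7.1.3 puts castrate testosterone at 2 to 4 weeks after initiation. For a start between 0 and 2 weeks after fiducials, castrate levels are reached between 0 + 2 = 2 and 2 + 4 = 6 weeks after fiducials. Section 7.1.10 (leuprolide) describes a rise in the first week. At LEAD these men may therefore have raised, falling or castrate testosterone, and the documents do not say which is usual.

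**The post-LEAD window.** It runs from 24 − 12 = 12 hr to 24 + 12 = 36 hr, a span of 24 hr. If the first IMRT fraction is given at the 32-hr limit, 36 − 32 = 4 hr of the window follows it (4/24, about 17%). If it is given at 24 hr (assumed: same time next day), 36 − 24 = 12 hr follows it (12/24 = 50%). In that second case 12 hr of the window remains before the fraction.

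**What each difference contains**

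- As planned, post-LEAD minus baseline = LEAD + seed placement (all) + biopsy and antibiotics (some) + ADT start (some) + first IMRT fraction (some) + drift over at least a week.
- With a day-1 sample, post-LEAD minus day-1 = LEAD + first IMRT fraction (if the draw is late) + whatever is still changing over 12 to 36 hr. Effects of seeds, biopsy or ADT that are stable by day 1 cancel.

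**Rationale against panel.** The rationale names TNF-alpha, TRAIL, PAR-4 and ceramide. Section 4.12 lists TNF-alpha by ELISA. TRAIL, PAR-4 and ceramide are in none of its FACS, RT-PCR or ELISA lists, and no other section names them as assays. Named overlap: 1 of 4.

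**The case against.** The strongest reply is that the protocol does not commit to this test. The four-mediator sentence is rationale, and Section 4.12 states its own purpose as activation of peripheral immunity. The neighbouring blood and urine work in Section 4.13 is called exploratory. This stands, and it limits the importance of the point.

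ADT and biopsy are optional, and ADT may precede consent. Men already on ADT give an on-treatment baseline, and men without ADT have no such confounder. This also stands. It leaves seed placement, which no treated patient avoids.

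The wait of at least a week may let a needle or antibiotic effect settle. That is possible: the documents give no evidence that such an effect persists to LEAD, and none that it does not. Only a sample on the day would show it.

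A reader might infer more: that the comparison cannot test LEAD-induced change at all, and that three of the four mediators will yield no data. The documents do not support either. A TNF-alpha change can be measured; what is weak is its attribution. On the mediators, Section 4.12 opens with "We will assess protein biomarkers and immune activation markers in the serum/whole blood samples of patients receiving high-dose LEAD RT" but itemises only the immune panel, Section 4.13 adds serum protein work without an analyte list, and plasma is frozen. The defensible statement is that the three are not named.

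**Conclusion.** The point holds as a confounding problem in an exploratory comparison. In every LEAD-treated patient (at most 25 pairs, fewer if LEAD is withheld after planning) the change spans seed placement and at least one week. In some it also spans biopsy, ADT start or the first IMRT fraction. The direction and size of the resulting bias cannot be derived from the documents, and more patients would not remove it. It would also be wrong to infer that ADT start separates the two samples in everyone, or that men are typically castrate by LEAD: the first contradicts Section 4.15, and the second needs a fiducial-to-LEAD interval that the plan does not state.

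The primary objective (feasibility and toxicity) and the listed secondary objectives do not use these blood samples and are unaffected. This is a cheap improvement to make, not a threat to the trial's main conclusions. The one assumption in the working is the 24-hr timing of the first IMRT fraction; the 4-hr overlap at the 32-hr limit follows from the protocol's own limits.

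**What to change.** Amend Sections 4.12, 5.1, 5.2 and Appendix I as follows.

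- Schedule the two Section 4.12 tubes (EDTA and SST) on day 1 immediately before LEAD. If 4 tubes are drawn before fiducials, move two of them and leave the rest for Section 4.13. If only 2 are drawn there, as footnote h allows, add two tubes on day 1.
- Draw the post-LEAD sample before the first IMRT fraction, within the existing 12 to 36 hr window. Where that is not possible, record that it followed a fraction. Only the blood draw moves; the treatment schedule does not change.
- Define the LEAD change as the post-LEAD value minus the day-1 pre-LEAD value in the same patient, and report it by ADT status on day 1.
- Align the mediator sentence in Section 1.4.5 with the assay list. Narrowing the sentence costs nothing. Adding TRAIL, PAR-4 and ceramide is optional and would need assay resources.

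The cost is a protocol amendment and one extra venepuncture on a day the patient already attends. There would be either fewer tubes at the earlier draw or two more tubes in total.

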5.2 Evaluations During Treatment

- High dose boost will be started on a Monday, Tuesday or Wednesday.
- Plasma and serum (up to 4 tubes) and urine (50 mL) will be collected for research (research fluids) at 24 hr post-LEAD RT and during the last week of RT.
- Weekly history and physical, evaluation of patient's ability to perform daily activities (Zubrod performance status; Karnovsky or ECOG performance status may be used to estimate Zubrod), and evaluation of toxicity.
- Blood (up to 4 tubes) will be drawn at RT completion during the last week of RT from a vein for the following tests:
 - Serum Testosterone.
 - Liver function tests (only if on ADT)
 - Complete cell counts
 - Lipid profile
- Quality of Life surveys will be administered during the last week of RT:
 - The Expanded Prostate Cancer Index Composite Questionnaire-SF12 (EPIC-SF12)
 - Memorial Anxiety Scale for Prostate Cancer patients (MAX-PC)
- International Prostate Symptom Index (IPSS) questionnaire during the last week of RT.

5.3 Post-treatment Evaluations (after RT) *Measurements and follow-up visits should occur ± 2 weeks up to the 3 month visit and ± 4 weeks for subsequent measurements/visits*

- History and physical, evaluation of patient's ability to perform daily activities (Zubrod performance status; Karnovsky or ECOG performance status may be used to estimate Zubrod), and evaluation of side effects at 6 weeks, 3 months, and then every 6 months for 5.25 years.
- Blood work (tubes of blood will be drawn at each follow-up as described below):
 - PSA at 6 weeks, 3 months and then every 6 months for 5.25 years.
 - Testosterone at 6 weeks, 3 months, and 9 months after radiotherapy. If testosterone remains abnormally low after ADT, tests will continue to be done at each follow-up visit.
 - BUN and creatinine to evaluate kidney function prior to MRIs at 3 months, 9 months and within 2 months prior to the 2-year prostate biopsy.
 - Liver function tests at 6 weeks and 3 months after radiotherapy (only at 3 months if not receiving ADT).
 - Complete blood counts at 3 months.
 - Lipid profile at 6 weeks, 3 months, 9 months, and within 2 months prior to the 2-year prostate biopsy.
- Plasma and serum (up to 4 tubes), and urine (50 mL) for research fluid tests will be obtained at 6 weeks, 3 months, 9 months and within 2 months prior to the 2-year prostate biopsy.
- Multiparametric MRI's of prostate/pelvis with timed contrast (if possible) at 3 months, 9 months, and within 2 months prior to the post-treatment prostate biopsies at 2 – 2.5 years post-completion of all therapy. The Eigen Artemis® system fusion software

(FDA approved) may be used to fine-tune the location of the tumor and biopsies by fusion of the previously obtained multiparametric MRI to the transrectal ultrasound in real time. The ultrasound is the true guidance imaging parameter that identifies the prostate boundaries and other nearby structures. The MRI is fused to the ultrasound such that the biopsies may be directed to a region in the ultrasound space.

- Bone scan at the discretion of treating physician.
- Quality of Life surveys:
 - The Expanded Prostate Cancer Index Composite Questionnaire-SF12 (EPIC-SF12) at 6 weeks, 3 months, 9 months, 15 months, and then yearly to 5.25 years
 - Memorial Anxiety Scale for Prostate Cancer patients (MAX-PC) at 6 weeks, 3 months, 9 months, 15 months, and yearly to 5.25 years
- International Prostate Symptom Index (IPSS) questionnaire at 6 weeks, 3 months, and then every 6 months for 5.25 years.

Note: Measurements and follow-up visits should occur \pm 2 weeks up to the 3 month visit and \pm 4 weeks for subsequent measurements/visits with the exception of the post-LEAD RT lipids and blood and urine collection for research, which is 24 hr \pm 12 hr.

5.4 Early Discontinuation of Therapy

See early stopping rules in Section 12.0

6.0 DOSING DELAYS/DOSE MODIFICATIONS

6.1 Study Agent

The study agent in this protocol is radiation, to be delivered in an innovative and investigational manner. The experimental component of the treatment is a single high-dose fraction of LEAD radiation, a dose of 12-14 Gy to be delivered to the multiparameter MRI identified tumor lesion(s). As described above, a standard radiation dose used for treatment of prostate cancer is 76 Gy at 2.0 Gy per day. This will be begun the day after the LEAD RT treatment (total dose for all treatments of 88-90 Gy and 149 Gy_{3.0} in 2.0 Gy equivalents).

6.2 Other Agent(s)

Lupron (leuprolide acetate), Zoladex (goserelin), Casodex (bicalutamide) and Eulexin (flutamide) or other equivalent generic agents are used in routine management of prostate cancer for androgen deprivation. These drugs are not study specific and are standard for prostate cancer; they will not be supplied by the pharmacy at SCCC.

Short term androgen deprivation (STAD) for 4-6 months (+/- 2 months) may be administered to some patients as described in sections 3.1 and 4.7. This timing is based on LHRH agonist injections (not the bicalutamide).

STAD will consist of oral antiandrogen administration and LHRH agonist injections to begin within the aforementioned timeframe. The antiandrogen will be either flutamide at 250 mg p.o. TID or bicalutamide at 50 mg p.o. QD. Antiandrogen therapy should begin at approximately the same time as LHRH agonist injection but may be started up to two weeks earlier. Antiandrogen administration will be given for up to four months. The length of STAD therapy will be pegged to the anticipated duration of LHRH agonist therapy. LHRH agonist injections (Lupron or Zoladex) may be given in any possible combination, such that the total LHRH agonist treatment time is 4-6 months (+/- 2 months). For example, LHRH agonist injection(s) may be

given as a single 4-month injection, a 4-month injection and one to two 1-month injection(s), two 3-month injections, one to three 1-month and a 3-month injection (4-6 months total), four to six 1-month injections, or a 6-month injection.

7.0 AGENT FORMULATION AND PROCUREMENT

7.1 Agents

Lupron, Zoladex, Casodex, Eulexin or other equivalent generic agents

7.1.1 Other names

- **Lupron** - leuprolide acetate
- **Zoladex** - goserelin
- **Casodex** - bicalutamide
- **Eulexin** - flutamide

7.1.2 Classification

- **Lupron** is a synthetic nanopeptide analog of naturally occurring gonadotropin-releasing hormone (*GnRH* or *LH-RH*). The analog possesses greater potency than the natural hormone.
- **Zoladex** is a LHRH analog with substitutions for the L-amino acid Glycine in positions 6 and 10.
- **Casodex** is a nonsteroidal antiandrogen which has no androgenic or progestational properties. The chemical name is Propanamide, N-[4-cyano-3(trifluoromethyl)phenyl]-3-[(4-fluorophenyl)sulphonyl]-2-hydroxy-2- methyl, (+,-).
- **Eulexin** is a substituted anilide. It is a fine, light, yellow powder, insoluble in water but soluble in common organic solvents such as aromatic or halogenated hydrocarbons. Its concentration in plasma can be determined by gas chromatography.

